7.1 Analysis Sets

The planned analyses as described in this SAP will be presented for the Enrolled Set (ES), Intent-To-Treat (ITT) population or the mobilisation set (MS). Definitions of these analysis sets can be found in Table 4.

Table 4 Definition of populations

Population	Label	Definition / Criteria	Analyses Evaluated [1]
ES	Enrolled Set	
• All patients for whom informed consent was obtained	Disposition summary table and listing of reasons for withdrawal
ITT	Intent-To-Treat Population	
• All patients treated with OTL-103 in this study with data available within the clinical database	
• Study Population• Efficacy
MS	Mobilisation Set	
• All patients who started peripheral blood stem cell (PBSC) mobilization or bone marrow harvest procedures	
• Safety

[1] Additional analyses may be performed on these analysis sets if required (e.g. Safety analyses in ITT set).

7.2 Covariates and Subgroups

No covariates and subgroups are planned to be used in the analyses due to the small sample size.

7.3 Missing Data

Considering the small sample size of the study, missing data will not be imputed unless otherwise indicated. Missing data will be reported as follows:

- These data will be indicated using a “blank” in subject listing displays. Unless all data for a specific visit are missing in which case the data are excluded from the table.
- Answers such as “Not applicable” and “Not evaluable” are not considered to be missing data and will be displayed as such.

For the evaluation of sustained engraftment, if data on peripheral blood (PB) CD3+ is not available, the missing CD3+ value will be imputed as the average of PB CD4+ and CD8+ values obtained from the same sample at that visit.

Completely missing start or end dates will remain missing, with no imputation applied. Consequently, time to onset and duration of such events will be missing. Partial dates will be displayed as captured in subject listing displays.

Partial dates for adverse events, medical history or concomitant medications records will be imputed for the purpose of assigning phase of onset and in the calculation of duration of adverse events.

The methods for dealing with partial start and stop dates are described below for adverse events and concomitant medications.

The answers to the question “Ongoing?” as recorded on the eCRF pages will also be taken into consideration to determine if the event continued post- gene therapy.

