4.3. Efficacy Endpoints

4.3.1. Primary efficacy endpoints

a) Overall survival

From day +1 to 3 years after gene therapy, and then monitored as part of the long-term follow up.

b) Sustained engraftment of genetically corrected hematopoietic stem cells in peripheral blood and/or in bone marrow

Presence of gene corrected cells assessed by quantitative PCR on peripheral blood and bone marrow cells at 1 year after gene therapy. Adequate engraftment is defined as ≥ 0.04 VCN/cell in BM CD34+ (equivalent to 4% assuming a VCN of 1) or ≥ 0.1 VCN/cell in peripheral blood T lymphocytes (equivalent to 10% assuming a VCN of 1).

c) Expression of vector-derived WASP

Presence of detectable vector-derived WASP expression at 1 year after gene therapy by FACS analyses and/or Western Blot.

In case of failure of engraftment of transduced cells in two or more patients, intensification of conditioning dose and increase in the minimal cell dose will be considered after an amendment to the study.

d) Improved T-cell functions

Improvement in in vitro T-cell proliferation upon stimulation with anti-CD3i mAbs at 1, 2, and 3 years after gene therapy as compared to pre-gene therapy values.

e) Antigen-specific responses to vaccinations

- Ability to mount a protective humoral response to nominal antigens, including antibodies to at least 4 out of 5 T cell dependent antigens tested (Tetanus Toxoid, Diphtheria, Hepatitis B, Pertussis, Haemophilus B) measured after the end of the vaccination schedule (foreseen >1 year after gene therapy). In case results are available on $n < 5$ antigens, the rule of at least $n-1$ will be applied for defining success.

- Ability to mount a protective humoral response to unconjugated polysaccharide antigens (Pneumococcus), measured after the end of the vaccination schedule (foreseen >1 year after gene therapy).

- Positive cellular response to Tetanus Toxoid after vaccination, measured by *in vitro* proliferative response >1 year after gene therapy.

f) Improved platelet count and normalization of MPV

Sustained increase in platelet count compared to baseline during the 3 year follow up, analyzing the individual longitudinal profile, according to the planned follow up visit and including platelet counts collected for clinical reasons during follow up (in transfusion independent patients).

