- g) **Bone marrow evaluation:** needle aspirate with immunophenotype: CD3+, CD3+/CD4+, CD3+/CD8+, CD19+, CD20+, CD22+, CD20+/CD22+, CD2+, CD16+/CD56+, CD19+/IgM+, CD19+/kappa, CD19+/lambda, CD71+/Glycophorin A+, CD15+, CD13+, CD38+/CD138+, CD61+, CD34+(ISHAGE), clonogenic progenitors (CFU-C), morphology, and karyotype. PCR analysis on transduced cells will be performed separately, including the assessment of %LV+ colony-forming cells (CFC) from patient's BM-derived clonogenic progenitors.
- h) **Microbiological evaluation:** **n°1:** Search for bacteria and fungi in nasal and pharyngeal swabs; CMV and EBV DNA search by molecular tests on PB plasma, stool culture, search for bacteria in the urine. **N°2:** Search for Legionella antigen in urine. Search for Bacteria, Mycobacteria, fungi, Pn. jirovecii, Legionella, Chlamydia pn. and Mycoplasma pn. in deep pharyngeal aspirates. Search for Respiratory Syncytial Virus (RSV) in nasal wash. Search for adenovirus in the blood (molecular test); search for parasites and enteroviruses in the stools. **N°3** Search for HSV1, HSV2, HHV6, HHV7, HCV, HBV, HIV genomes in the PB plasma (molecular test).

- i) **Immunological evaluation n°1:** Immunophenotype with lymphocyte subpopulations (CD45+, CD14+, CD3+, CD3+/CD4+, CD3+/CD8+, CD19+, CD2+, CD16+/CD56+, percentage and absolute count. Serum immunoglobulins (IgG, IgA, IgM, total IgE). **n°2:** Immunophenotype with lymphocyte subpopulations (CD3+, CD4+, CD8+, CD16+, CD56+, CD14+, CD45+, TCR1+ (alfa/beta), TCR2+ (gamma/delta), CD4+/CD45RA+ & CD45RO+, CD8+/CD45RA+ & CD45RO+, CD4+/DR+, CD8+/DR+, CD4+/CD25+, CD8+/CD25+, CD3+/CD4+, CD3+/CD8+, CD19+, CD2+, CD16+/CD56+, kappa+, lambda+) percentage and absolute count. Serum immunoglobulins (IgG, IgA, IgM, total IgE). **n°3:** Proliferative response to mitogens (PHA, anti-CD3i, anti-CD3i+anti-CD28, IL-2, PWM). **n°4:** Proliferative response to Candida and alloantigens. Proliferative response to tetanus toxoid (if patient was vaccinated). Dose response of proliferation after anti-CD3i stimulation on PBMC and/or T-cell lines. TCR repertoire studies in the peripheral blood by FACS (Vbeta repertoire). **n°5** In patients who discontinued IVIG (as described in Section 6.11), a vaccination program will be started. Serum antibody levels to vaccinal antigens (tetanus toxoid, diphtheria, hepatitis B, Pneumococcus, Pertussis, Haemophilus B) or pathogens (EBV VCA, CMV, measles, rubeola, VZV, HSV) will be measured.

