- j) **Autoimmunity evaluation**, searching organ-specific and systemic antibodies in the serum: anti-platelet antibodies, anti-nuclear antibodies (ANA); anti-extractable nuclear antigens antibodies (ENA), if ANA positive; anti-neutrophil cytoplasmic antibodies (p-ANCA, c-ANCA); anti-DNA antibodies (ADNA); anti-mitochondrial antibodies (AMA); anti smooth muscle antibodies (ASMA), anti-Liver-Kidney-Muscle (LKM); Coombs' tests (direct/indirect).
- k) **Evaluation of the presence of genetically modified cells.** Vector copy number (measured by quantitative PCR as VCN/cells) will be done after gene therapy in total nucleated cells (day +14), and afterwards in PB lymphocyte subpopulations (CD3+ and/or CD4+ and CD8+ T lymphocytes, B lymphocytes, NK cells) and granulocytes and in bone marrow cell subpopulations (CD15+, GlyA+, CD3+, CD19+, CD56+, CD34+).
- l) **Archiving of samples.** Samples from peripheral blood and bone marrow (serum, plasma, cell pellets, viable cells in DMSO, cell lines, DNA) will be archived stored at -80° at SR-TIGET, according to Institutional guidelines.
- m) **Platelet activation and morphology:** For platelet activation, the expression of activation markers on the surface of peripheral blood-derived platelets after stimulation with agonists will be assessed. For platelet morphology, the platelet perimeter, area and ultrastructure will be assessed by transmission electron microscopy.

Repeat or unscheduled samples may be taken, or tests performed, for safety reasons or due to technical issues with the samples or tests.

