9. ASSESSMENT OF EFFICACY

9.1. Sustained engraftment of genetically corrected cells in peripheral blood and/or in bone marrow

Positive engraftment will be assumed as detectable gene corrected cells on peripheral blood and bone marrow cells at 1 year after gene therapy. Adequate engraftment is defined as $\geq 4\%$ CD34+ cells (equivalent to 0.04 VCN/cell) in the bone marrow or $\geq 10\%$ peripheral blood T lymphocytes or peripheral blood mononuclear cells (when cells are not sufficient) (equivalent to 0.1 VCN/cell). This value is based on clinical experience in other gene therapy trials, which has demonstrated 4% average long-term engraftment of autologous hematopoietic stem/progenitor cells transduced with retroviral vectors in the bone marrow of paediatric patients with ADA-SCID and receiving reduced intensity, non-myeloablative conditioning ([Aiuti et al., 2009](#); unpublished results).

To further confirm results, the PB T cell or PB MNC cells and the pre-GT sample will be performed at MolMed S.p.A.

In addition, the multilineage engraftment will be evaluated in BM and/or PB subpopulations (BM subpopulations: GlyA+, CD15+, CD3+, CD19+, CD56+; PB subpopulations: CD15+, CD19+, CD56+). If data on PB CD3+ are not available, the average of PB CD4+ and PB CD8 T cells will be calculated and reported as T-cell engraftment. Adequate multilineage engraftment is defined as $\geq 4\%$ in all the available cells (equivalent to 0.04 VCN/cell).

Assessment parameter: PCR for transduced cells (specific for lentiviral vector sequences).

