9.1.1 Overall Survival

Overall survival is defined as the time in days from gene therapy to date of death. Subjects alive at the end of follow-up or having not yet reached the defined follow-up phase will be censored at the latest time point for which vital status information is available. Follow-up will be defined as all data up to the data cut or end of study depending upon availability of data per patient.

The Kaplan-Meier estimate of survival for the entire duration of follow up will be obtained, with 95% confidence interval (CI) if there is any fatal event. The analysis results will be presented in a graph as well as a table. A listing of fatal events will be reported as a safety display.

9.1.2 Engraftment of genetically corrected hematopoietic stem cells in peripheral blood and/or in bone marrow

Adequate engraftment of genetically corrected cells in peripheral blood and/or in bone marrow is defined as ≥ 0.04 VCN/cell in bone marrow CD34 $^{+}$ or ≥ 0.1 VCN/cell in peripheral blood T Lymphocytes CD3 $^{+}$ at 1 year after gene therapy.

Missing PB CD3 $^{+}$ values will be imputed using the mean PB CD4 $^{+}$ and PB CD8 $^{+}$ values obtained from the same sample at that visit. If insufficient data are available to determine an adequate engraftment, the response will be set to missing. This includes two scenarios:

- Neither BM nor PB samples provides data for engraftment assessment;
- Values are below the threshold for the respective sample matrix (BLQ).

A summary table detailing the number and percentage of subjects who present with adequate engraftment at 1 year after gene therapy will be generated, with the 95% CI of the percentage calculated. PCR transduced cell evaluation in BM and PB will be summarised with descriptive statistics and graphs. Time to adequate engraftment will be plotted and listed based on VCN in BM and PB. The percentage of lentiviral vector (LVV) transduced colony forming units (CFU) in bone marrow cells (%LV in BM) will also be tabulated and plotted.

The longitudinal profile of the PCR transduced cell evaluation in BM and PB over time will be presented in a listing and a plot.

A box plot will be created for engraftment (PB CD3⁺ and BM CD34⁺ VCN/cell) by treatment source (BM or PB) at each year post gene therapy.

Scatterplots will be presented of treatment dose (CD34+/kg), busulfan dose (AUC), and age at treatment against engraftment (PB CD3⁺ and BM CD34⁺ VCN/cell) at each year post gene therapy.

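### A missing T-cell VCN is filled with the unweighted CD4+/CD8+ mean, which misses the pooled value when both subset counts and subset VCNs differ; minor, but it can decide the 0.1 T-cell limb

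*SAP*

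**What the plan says.** For the evaluation of sustained engraftment, SAP 7.3 provides that if the CD3+ result is unavailable, "the missing CD3+ value will be imputed as the average of PB CD4+ and CD8+ values obtained from the same sample at that visit". SAP 9.1.2 repeats this inside the primary engraftment definition (missing CD3+ "values will be imputed using the mean PB CD4"+ and CD8+ values). Protocol 9.1 has the same rule: "the average of PB CD4+ and PB CD8 T cells will be calculated and reported as T-cell engraftment". None of the three mentions weights, a flag for imputed values or a sensitivity analysis.

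The T-cell value feeds a two-limb criterion at 1 year (Protocol 4.3.1, SAP 9.1.2). A patient is adequately engrafted with at least "0.04 VCN/cell in bone marrow CD34"+ cells, or with at least 0.1 VCN/cell in peripheral blood T cells. SAP 9.2.2 then applies the criterion over the whole follow-up, with a summary each year.

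Protocol 7.2 k) measures blood VCN in "CD3+ and/or CD4+ and CD8+ T lymphocytes, B lymphocytes, NK cells" and granulocytes, so a visit with CD4+ and CD8+ results but no CD3+ result is an accepted pattern. Protocol 7.2 i) also collects subset sizes: "CD3+/CD4+, CD3+/CD8+, CD19+, CD2+, CD16+/CD56+, percentage and absolute count".

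**The concern.** VCN per cell in a mixed population is the mean of the subset VCNs weighted by subset size. An equal-weight average treats CD4+ and CD8+ cells as equally numerous whatever the counts show. If the larger subset also carries a different VCN, the imputed value is pulled towards the smaller one. That value is then compared with a fixed cut-off, so a small error can decide the T-cell limb for a patient close to 0.1. With eight patients, one changed classification is visible in the estimate and its interval. The weights needed to avoid the problem are already collected.

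**Working it through.** The plan gives no worked imputed value, so there is no figure to reproduce.

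**Inputs from the documents.** Cut-offs of 0.1 (blood T cells) and 0.04 (marrow CD34+), joined by OR; n = 8; Wilson 95% intervals.

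**Inputs assumed.** The VCNs V4 (CD4+) and V8 (CD8+), and the CD4:CD8 count ratio r. The documents give none of these. The CD4 share is w = r/(1 + r).

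**Formulas.**
- Pooled CD4+/CD8+ VCN = w × V4 + (1 − w) × V8
- Plan's value = (V4 + V8)/2
- Plan minus pooled = (0.5 − w) × (V4 − V8)

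The difference vanishes if w = 0.5 or if V4 = V8. An error therefore needs both unequal counts and unequal VCNs.

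**Numbers.**

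| V4 | V8 | Plan's value | Pooled value |
|---|---|---|---|
| 0.15 | 0.06 | 0.105 | 0.078, 0.087, 0.096, 0.105, 0.114, 0.123 at w = 0.2, 0.3, 0.4, 0.5, 0.6, 0.7 |
| 0.14 | 0.05 | 0.095 | 0.104 at r = 1.5; 0.110 at r = 2 |
| 0.08 | 0.13 | 0.105 | 0.097 at r = 2 |
| 0.10 | 0.10 | 0.100 | 0.100 at any r |
| 0.50 | 0.30 | 0.400 | 0.35 to 0.45 for r from 0.33 to 3 |

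In the first row the plan's value and the pooled value fall on opposite sides of 0.1 at shares of 0.2 to 0.4, and on the same side at 0.5 to 0.7. The second row crosses upwards and the third downwards. The last two rows do not cross.

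**How close to 0.1 the plan's value must be.** With a 2-fold VCN difference and r = 2, pooled/plan is (2/3 × 2 + 1/3 × 1)/1.5 = 1.111, or (2/3 × 1 + 1/3 × 2)/1.5 = 0.889 with the VCNs reversed. A crossing is possible for plan values from 0.1/1.111 = 0.090 to 0.1/0.889 = 0.1125. The same calculation gives 0.096 to 0.104 (1.5-fold, r = 1.5) and 0.080 to 0.133 (3-fold, r = 3).

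**Effect on 1-year status.** With marrow CD34+ at 0.02, a T-cell value of 0.095 fails and 0.11 passes. With marrow at 0.04 or above, the patient passes either way. With marrow missing, the T-cell value decides.

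**Later years.** Protocol 8.4.2 places the marrow aspirate at years 5 and 8 after year 3, and the SAP Appendix 3 long-term schedule leaves that column blank at years 4, 6 and 7. SAP 9.1.2 says: "If insufficient data are available to determine an adequate engraftment, the response will be set to missing". One case it lists is that neither marrow nor blood provides data. Where blood alone provides data, the T-cell limb therefore stands alone.

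**Effect on the estimate.** One patient in eight is 12.5 points: 8/8 has a Wilson interval of 67.6% to 100%, and 7/8 (87.5%) has 52.9% to 97.8%.

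**Limit of the weighted value.** It covers CD4+ and CD8+ cells only. Assume V4 = 0.12, V8 = 0.09 and r = 2, so the pooled value is 0.110. If 10% of CD3+ cells are neither CD4+ nor CD8+, with VCN 0, 0.05 or 0.10, the CD3+ VCN is 0.9 × 0.110 + 0.1 × that VCN = 0.099, 0.104 or 0.109.

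**The case against.** The strongest reply is that the 1-year result is well protected. Marrow is scheduled at 1 year, and a patient at or above 0.04 in marrow CD34+ counts as engrafted whatever the imputed T-cell value. Status changes only if CD3+ is missing, marrow is below 0.04 or missing, the T-cell value is near 0.1, and the subsets differ in both count and VCN. This stands for 1 year. It does not cover years 4, 6 and 7.

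The examples rest on VCNs chosen near the cut-off. The documents give no VCN values, CD4:CD8 ratios or frequency of missing CD3+. A reader might infer that the primary result is probably biased, or that patients are likely to be misclassified. The documents do not support that: a crossing is shown to be possible, not likely. A reader might also take the weighted figure for the true CD3+ VCN. It is not, because it leaves out CD3+ cells that are neither CD4+ nor CD8+.

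The rule is also prespecified and the same in both documents. Enrolment was planned over 5 years from April 2010 and the SAP follows the September 2023 protocol, so 1-year values are probably already known in this open-label study. Replacing the rule silently would be post hoc. This stands, and it is why both results should be shown.

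Finally, the SAP does not say outright that imputed values enter the descriptive VCN summaries and plots; SAP 7.3 limits the imputation to sustained engraftment. Protocol 9.1, however, has the average reported as T-cell engraftment, so it is at least a reported value. The SAP lists individual PCR and immunophenotype results, which helps a reader to check a borderline patient, but it plans no flag showing which values were imputed.

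**Conclusion.** The point holds and is minor. The simple average departs from the pooled CD4+/CD8+ VCN whenever both the counts and the VCNs of the two subsets differ. Under the assumed differences it can fall on the wrong side of 0.1 when it lies within roughly 4% of the cut-off (1.5-fold VCN difference, r = 1.5) to 20% below or 33% above it (3-fold, r = 3). The 0.1 value is not a stand-alone primary cut-off: at 1 year the error matters only where marrow CD34+ is below 0.04 or missing. It has more room to act at years 4, 6 and 7 and in the reported T-cell VCN. The analysis is descriptive and unpowered, and its intervals are nominal, so no formal inference is at risk.

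**What to change.** In SAP 7.3 and 9.1.2, compute the imputed peripheral blood CD3+ VCN as (nCD4 × VCN CD4 + nCD8 × VCN CD8)/(nCD4 + nCD8), using absolute counts from the same visit, and note that it omits CD3+ cells that are neither CD4+ nor CD8+. Use the simple average only if the counts are missing. In addition:

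- flag every imputed value in listings and tables;
- show the engraftment result under the prespecified simple-average rule next to the weighted one;
- for each patient with an imputed value, state whether marrow CD34+ alone met the criterion;
- record the change as a departure from Protocol 9.1 as well as in the two SAP sections.

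No new data are needed. Protocol 8.4.2 schedules CD4 and CD8 flow cytometry together with VCN PCR every 6 months for 3 years and yearly from year 4 to year 8. The cost is a documented departure from a prespecified rule and a small amount of programming.

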7.3.1 Partial Date Conventions

Partial dates for adverse events and concomitant medications may be imputed for statistical analyses according to the following rules. Imputed dates will not be shown in the listings, but Study Day based on imputation should be displayed.

Reference date of prior and concomitant medications, and adverse events is date of gene therapy. Reference date of adverse events taken from medical history is the date of first signed informed consent.

Imputation of partial start dates:

- If only the month and year are specified and the month and year of reference date is not the same as the month and year of the start date or the reference date is missing, then use the 1st of the month.
- If only the month and year are specified and the month and year of reference date is the same as the month and year of the start date, then use the reference date. If this results in an imputed start date that is after the specified end date and the specified end date is before the date of informed

consent, then use the 1st of the month; else if the specified end date is on or after the date of informed consent, then use the date of informed consent.

- If only the year is specified, and the year of reference date is not the same as the year of the start date or the reference date is missing, then use January 1 of the year of the start date.
- If only the year is specified, and the year of reference date is the same as the year of the start date, then use the reference date. If this results in an imputed start date that is after the specified end date, then use January 1 of the year of start date.
- If the start date is completely unknown, then use the reference date or the date of informed consent if the reference date is missing. If this results in an imputed start date that is after the specified end date, then use January 1 of the year of reference date, the informed consent date or the year of the end date, whichever is earlier.

Imputation of partial stop dates:

- If only the month and year are specified, then use the last day of the month.
- If only the year is specified, then use December 31 of that year.
- For medications: If the stop date is completely unknown, do not impute the stop date. In this case the medication is assumed to be a concomitant medication and would be presented in the outputs as such, but no Study Day will be presented in the listing for stop date.
- For adverse events: If the stop date is completely unknown, do not impute the stop date and do not present Study Day in the listing. Adverse events will be summarised according to the phase in which the AE started.

Imputation of partial date of diagnosis for calculation of the time since diagnosis:

- If only the month and year are specified, use the first day of the month.
- If only the year is specified, use the 1st Jan of that year.
- If either of the above result in a start date that is prior to the subject's date of birth then use the subject's date of birth.

